### 11.1.2. Time to Response (TTR)

Time to response is define as time from Cycle 1 Day 1 to the date of first best overall confirmed response of CR or PR and will be summarized as a continuous outcome. Subjects without CR or PR as the best confirmed response are not included in the TTR summary. Summary of TTR may not be generated if there are not enough subjects with responses to create meaningful summaries.

### 11.1.3. Duration of Response (DOR)

Duration of response is defined as time from the first best overall confirmed response of CR or PR to the date of disease progression or death. If a subject did not experience the event, DOR will be censored. The event and censoring rules for DOR will be the same as the rules for PFS ([Section 11.3](#)). DOR will be analyzed using the Kaplan-Meier method. The output will include count and percentage of subjects with events or censored outcome including the type of event and censoring. Median DOR and 95% CI based on log-log transformation will be provided. Landmark analyses of DOR at various timepoints may be carried out if of clinical interest. Kaplan-Meier plot supporting the table summary may also be generated.

Subjects without CR or PR as the best confirmed response are not included in the DOR analyses. Summary of DOR may not be generated if there are not enough subjects with responses to create meaningful summaries.

### 11.1.4. Duration of Stable Disease

Duration of stable disease is defined as time from Cycle 1 Day 1 to the date of disease progression or death. If a subject did not experience the event, duration of stable disease will be censored. The event and censoring rules for duration of stable disease will be the same as the rules for PFS ([Section 11.3](#)). Duration of stable disease will only be presented in the listing that supports the exploratory efficacy analyses.

Duration of disease is only defined for subjects with any CR, PR, or SD prior to the first PD or subjects who did not experience PD.

### 11.1.5. Change in Target Tumor Size

At each timepoint of imaging assessment the sum of the longest diameter of all the target lesions are derived. The change and percentage change from baseline to the post-baseline nadir will be summarized. A waterfall plot of best percent change from baseline (from baseline to nadir) by tumor type cohorts will be provided.

### 11.1.6. Response Criteria for mCRPC Subjects

In addition to the RECIST criteria, response for subjects with mCRPC will also be evaluated by prostate specific antigen (PSA) and Circulating Tumor Cell (CTC). The PSA and CTC data will be presented in listings for mCRPC subjects to facilitate the review of the responses.

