Statistical methods and analyses (cont'd):	
The analysis of all efficacy endpoints will be based on the Response Evaluable Population and will be evaluated using RECIST v1.1 criteria, or for subjects with NHL, the revised International Working Group (IWG) criteria (Cheson 2007), or for subjects with mCRPC, using a composite response rate defined as any one of the following (Scher 2016): A) Response based on RECIST v1.1; B) PSA decrease of $\geq 50\%$; or C) CTC count conversion. Absolute values for PSA and CTCs will be recorded at baseline and response will be analyzed based on percentage of change.
 
The ORR will be summarized using binomial proportions and confidence intervals computed by the method of Wilson. Duration of response (DOR) is defined as the interval from the first documentation of objective response (of partial response or complete response) to the earlier of the first documentation of PD or death from any cause. Analysis of DOR will be performed using the Kaplan-Meier method. Medians and other quartiles for DOR will be estimated in addition to the corresponding 2-sided 95% confidence intervals. Other efficacy variables will be further defined in the statistical analysis plan.
 
The PK parameters will be determined using non-compartmental method(s). Parameters, such as AUC_{inf}, AUC_{tau}, C_{min}, C_{max}, T_{max}, $t_{1/2}$, will be estimated and reported, as appropriate.
 
Pharmacodynamic parameters utilizing blood and tumor tissue to analyze biomarkers to identify possible predictors of clinical outcome will be further defined in the statistical analysis plan.

---	--

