11.2.3 EFFICACY ANALYSES

The analysis of all efficacy endpoints will be based on the Response Evaluable Population.

Efficacy endpoints will be evaluated using RECIST v1.1 criteria, or for subjects with NHL, the revised IWG criteria ([Cheson 2007](#)), or for subjects with mCRPC, a composite response rate defined as any one of the following ([Scher 2016](#)):

- Best response based on RECIST v1.1
- PSA decrease of $\geq 50\%$

- CTC count conversion

Absolute values for PSA and CTCs will be recorded at baseline and response will be analyzed based on percentage of change.

Descriptive analyses of the distribution of ORR, DCR, DOR, TTR, TTP, PFS per RECIST v1.1, the revised IWG criteria, or a composite of any one of the following:

A) Response based on RECIST v1.1; B) PSA decrease of $\geq 50\%$; or C) CTC count conversion, as applicable, and OS will be prepared.

The ORR will be summarized using binomial proportions and confidence intervals computed by the method of Wilson. The examples below display the CI estimates for response within each indication-specific group of approximately 20 enrolled to an expansion cohort. i.e. at the 95% CI, 0 of 20 responses observed excludes an ORR of 16%.

Numerator	Denominator	Proportion	Lower	Upper
0	20	0	0	0.161
1	20	0.05	0.009	0.236
2	20	0.10	0.028	0.301
3	20	0.15	0.052	0.360
4	20	0.20	0.081	0.416
5	20	0.25	0.112	0.469
6	20	0.30	0.145	0.519
7	20	0.35	0.181	0.567
8	20	0.40	0.219	0.613
9	20	0.45	0.258	0.658
10	20	0.50	0.299	0.701
11	20	0.55	0.342	0.742
12	20	0.60	0.387	0.781
13	20	0.65	0.433	0.819
14	20	0.70	0.481	0.855
15	20	0.75	0.531	0.888
16	20	0.80	0.584	0.919
17	20	0.85	0.640	0.948
18	20	0.90	0.699	0.972
19	20	0.95	0.764	0.991
20	20	1	0.839	1

The distribution of DOR, in the subset of subjects responding will be summarized using Tukey's five number summary, including the minimum, mean, median, maximum and

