## 4. STUDY ENDPOINTS

Study endpoints corresponding to the study objectives are listed below. Secondary endpoints and exploratory endpoints will be summarized and analyzed in separate reports and analysis plan for those endpoints will not be included in this document. As a result, the analysis datasets and outputs corresponding to these endpoints will not be included within the scope of this SAP.

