### 4.1. Primary Endpoints

- Safety parameters including adverse events (AEs), laboratory tests, and vital signs
- MTD: the highest dose at which  $\leq 33\%$  of subjects have a dose limiting toxicity (DLT) in a cohort of up to 6 subjects
- Recommended Phase 2 Dose (RP2D)
- Objective response rate (ORR)
- Disease control rate (DCR)
- Time to response (TTR)
- Duration of response (DOR)
- Progression-free survival (PFS)
- Time to progression (TPP)

- Overall survival (OS)

If there are no subjects with response (complete or partial response), TTR and DOR related summaries and listings will not be generated.

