### 11.1. Overall Response

#### 11.1.1. Overall Response Rate

Overall response rate will be assessed by the investigator per RECIST criteria version 1.1. Partial or complete response should be confirmed by a repeat tumor imaging assessment not less than 4 weeks from the date the response was first documented. The confirmed responses will be derived based on the overall responses by timepoint using the logics below:

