**Table 3: Confirmed Response per RECIST 1.1**

Initial Response	Subsequent Timepoint	Confirmed Response
Complete Response (CR)	CR at least 4 weeks after initial CR (or consecutive CRs with at most one NE in between with the last CR at least 4 weeks after initial CR)	CR
	CR less than 4 weeks	SD

Initial Response	Subsequent Timepoint	Confirmed Response
	PD or Not Evaluable (NE) or no subsequent assessment	SD if CR is at least 6 weeks from Cycle 1 Day 1, otherwise PD or NE
Partial Response (PR)	PR/CR at least 4 weeks after initial PR (or consecutive PRs/CRs with NEs in between with the last PR/CR at least 4 weeks after initial PR)	PR
	PR/CR less than 4 weeks, or SD	SD
	PD or NE or no subsequent assessment	SD if PR is at least 6 weeks from Cycle 1 Day 1, otherwise PD or NE
Stable Disease (SD)	PD or NE, SD, or no subsequent assessment	SD if SD is at least 6 weeks from Cycle 1 Day 1, otherwise PD or NE
Progressive Disease (PD)	Any assessment or no subsequent assessment	PD

The best overall confirmed response will be the best confirmed response from the above following the order of CR > PR > SD > PD > NE

The best overall response will be summarized for the following endpoints with count and percentage:

- CR
- PR
- SD
- PD
- NE
- ORR (CR + PR) with 95% CI (Wilson method [1])
- DCR (CR + PR + SD) with 95% CI (Wilson method)

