## 13. CHANGES FROM ANALYSES PLANNED IN THE PROTOCOL

The following are the changes from the analyses planned in the protocol

- Protocol section 3.6 defined 6 indication-specific cohorts in the expansion phase. The summaries based on the disease types will be adjusted based on the actual enrollment. Refer to [Section 9.2.1](#) for the definition of each disease type.
- Exploratory objectives and endpoints related to biomarkers in protocol Section 3.1.3 and SAP [Section 4.3](#) were not collected in the study.
- In protocol Section 3.1.3 and SAP [Section 4.3](#) one of the exploratory endpoints is “Association of QT, QTc, blood pressure, heart rate, other ECG intervals with time-matched PK concentrations. Profile of QTc over the dosing interval”. A summary PK report and QTc report will be provided in the clinical study report, but separate analysis of the endpoints listed here will not be done.
- In protocol Section 11 and SAP [Section 6.1](#) timing of interim analyses are specified. These interim analyses will not be presented and justification will be provided in the clinical study report.
- Alternative definition of response evaluable population was added in [Section 8.2](#).

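### The SAP plans no estimate of the protocol's composite response rate for mCRPC, and Section 13 does not declare the omission

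*SAP*

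**What the plan says.** **Protocol.** Section 11.2.3 specifies, for mCRPC, "a composite response rate defined as any one of the following": best response by RECIST 1.1, a PSA fall of 50% or more, or CTC conversion. The synopsis says the same ("using a composite response rate defined as any one of the following"). Section 11.2.3 then names this composite, where applicable, for ORR, DCR, DOR, TTR, TTP and PFS. ORR belongs to a primary objective (protocol 3.1.1, SAP 4.1).

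**SAP.** Section 11.1.1 states: "Overall response rate will be assessed by the investigator per RECIST criteria version 1.1". Table 3 and the summary under it derive ORR and DCR, with Wilson intervals, from confirmed RECIST responses. Section 11.1.6 first says that PSA and CTC are to be used, on top of RECIST, in judging mCRPC response. It then says only: "The PSA and CTC data will be presented in listings for mCRPC subjects to facilitate the review of the responses". Section 13 opens with "The following are the changes from the analyses planned in the protocol" and gives five items: disease-type grouping, exploratory biomarkers, the exposure-QTc endpoint, interim reviews, and the alternative evaluable definition.

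**Who is analysed.** Inclusion criterion 8 lets an mCRPC subject enter the expansion phase on measurable disease, on rising PSA, or on at least 5 CTCs per 7.5 mL. Protocol 11.1.2 and SAP 8.2 (under both dosing definitions) make measurable disease a condition of the Response Evaluable Population, with no mCRPC exception.

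**The concern.** A reader of the protocol expects an mCRPC response rate that counts PSA and CTC responses. A reader of the SAP outputs will find a RECIST rate and two listings, and nothing in Section 13 to explain the difference. If the SAP is followed as written, a response by PSA or CTC contributes to no rate and no interval, even in a subject with measurable disease.

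The population definition adds to this. Subjects admitted on PSA or CTC alone are those for whom the marker components are the natural response measures. On the literal wording they are absent from every efficacy output, including the PSA and CTC listings, because those listings are assigned to the response population.

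At stake is the completeness of one of six expansion cohorts in a descriptive trial. No hypothesis test or stopping decision depends on it.

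**Working it through.** **1. Protocol against SAP outputs**

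| Item | Protocol 11.2.3 and synopsis | SAP |
|---|---|---|
| mCRPC response | RECIST, PSA or CTC | RECIST 1.1 (11.1.1, Table 3) |
| Rate and 95% CI | ORR with Wilson interval | Table 14.2.1.1, RECIST only; no other response-rate table |
| PSA and CTC response data | Components of the composite | Listings 16.2.2.8 and 16.2.2.9 |
| PSA threshold | Fall of at least 50% | Not stated |
| CTC conversion rule | Named, not defined | Not stated |
| Declared in Section 13 | n/a | No |

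PSA has one other use. SAP 12.4 and Table 14.3.3.5 summarise values and change from baseline by visit in the Safety population. That is not a proportion of subjects with a 50% fall.

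**2. The protocol's own interval table**

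The Wilson limits are [p + z²/2n ± z√(p(1−p)/n + z²/4n²)] / (1 + z²/n), with z = 1.96 and n = 20 (protocol 11.2.3).

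- 0/20: the upper limit reduces to z²/(n + z²) = 3.84/23.84 = 0.161.
- 4/20: centre (0.20 + 0.096)/1.192 = 0.248, half-width 0.168, limits 0.081 to 0.416.

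Both agree with the printed table, as do the other 19 rows.

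**3. Same subjects in both rates**

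Let r be RECIST responders and m marker-only responders among n subjects, with the same confirmed RECIST response used in both rates. The composite is (r + m)/n, which is at least r/n. Each marker-only responder adds 1/n; at n = 20 that is 1/20 = 5 points. The documents do not give m. With r = 0 and assumed m:

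| m (assumed) | SAP rate (95% CI) | Composite (95% CI) |
|---|---|---|
| 0 | 0% (0 to 16.1) | 0% (0 to 16.1) |
| 1 | 0% (0 to 16.1) | 5% (0.9 to 23.6) |
| 2 | 0% (0 to 16.1) | 10% (2.8 to 30.1) |
| 4 | 0% (0 to 16.1) | 20% (8.1 to 41.6) |

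**4. Set widened to subjects without measurable disease**

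Let n1 subjects have measurable disease, with r RECIST responders. Let n2 not have it, and let M be all marker-only responders. The SAP rate is r/n1 and the composite is (r + M)/(n1 + n2). The composite is lower whenever M/n2 < r/n1. With assumed r = 2 and n1 = n2 = 10, the SAP rate is 2/10 = 20%. The composite is 2/20 = 10% if M = 0, 4/20 = 20% if M = 2, and 6/20 = 30% if M = 4. The direction is therefore not fixed.

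**5. Precision if such entrants are excluded and not replaced**

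For assumed shares of 20%, 40% and 60% in a cohort of 20, the evaluable n is 16, 12 and 8. The upper limit at zero responses, z²/(n + z²), is then 0.194, 0.242 and 0.324, against 0.161 at n = 20.

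**The case against.** **The SAP keeps PSA and CTC in view.** A reader might infer that the SAP withdraws the composite. It does not: 11.1.6 retains the intention to evaluate both markers. What is missing is a threshold, a derived variable and a rate. The composite is dropped by omission.

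**Other clauses might cover it.** SAP Section 4 says: "Secondary endpoints and exploratory endpoints will be summarized and analyzed in separate reports". ORR is primary, so that clause does not reach it. The biomarker item in Section 13 concerns the exploratory endpoints of protocol 3.1.3, which it says were not collected; PSA and CTC are planned as listings.

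**The protocol is not of one voice.** Appendix 2 describes response by RECIST, or by the lymphoma criteria for NHL, and says that a marker by itself does not establish an objective response. This stands in part. Section 11.2.3 and the synopsis are the more specific text for mCRPC, but Appendix 2 is a good reason to give the composite its own table and not to merge it into RECIST ORR.

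**Eligibility and analysis sets may differ.** It is tempting to call SAP 8.2 a flat contradiction of criterion 8. That is too strong. Protocol 3.8.2 allows non-evaluable expansion subjects to be replaced, and 11.1.2 points back to Section 4, which contains criterion 8. Against that, criterion 8 itself distinguishes measurable from otherwise evaluable disease, and Appendix 2 defines measurable disease by at least one measurable lesion. The literal reading is the more natural one, but it yields a mismatch to be reconciled. It originates in the protocol.

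**All results are descriptive.** True (protocol 11.2.1, SAP 9.1.2). This limits the severity but does not remove the need to report or declare a primary result.

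**Conclusion.** The point holds. The SAP, as written, produces no composite, PSA or CTC response rate for mCRPC, and Section 13 does not tell the reader. The population mismatch is a related, secondary matter inherited from the protocol. It should be fixed, but it affects one cohort of six and does not threaten the trial as a whole.

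The size is unknown and could be nil, because the documents give neither the number of marker-only responders nor the number of entrants without measurable disease. The gain of 5 points per marker-only responder assumes a fixed set of 20. A reader might infer that the SAP's RECIST rate must understate the composite. That is assured only in the same subjects; under a wider evaluable set the composite may be higher or lower.

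A reader might also want to extend the point to the OS and PFS population, since protocol 11.2.3 places all efficacy endpoints on the Response Evaluable Population and later speaks of all subjects for OS and PFS. The later sentences can be read as censoring statements within that population, and the question concerns every tumor type. It does not support this finding and, if raised, should be raised separately.

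**What to change.** 1. Add one mCRPC table with the composite response rate and Wilson 95% CI, and each component (RECIST, PSA, CTC) with its own denominator stated. Keep RECIST ORR as planned.
2. For that table and the PSA and CTC listings, define an mCRPC evaluable set consistent with inclusion criterion 8, in which a post-baseline PSA or CTC result counts as an assessment. Apply it to escalation and expansion subjects alike, since SAP 9.2.1 pools them by tumor type.
3. Before computing anything, write down the CTC-conversion definition and its denominator, and whether PSA or CTC response needs confirmation, consistent with the working-group reference the protocol cites for the composite. Appendix 7 defines rising PSA for entry only. Label these rules post hoc if response data have already been reviewed. SAP Table 1 quotes terms from the clinical database, which shows some data had been seen but not that response data had.
4. In Section 13, declare the evaluable set, and declare that DCR, DOR, TTR, TTP and PFS in mCRPC do not use the composite that protocol 11.2.3 also names for them. If the composite is not to be estimated, say so there and justify it.

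The cost is one table, one population flag, two listings moved to a wider population, and a few lines of text. No new data collection is needed: PSA and CTC are already scheduled at baseline and every 4 weeks (protocol 7.2.1 and 7.2.2).

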## 11.2. Time to Progression (TTP)

Time to progression is defined as time from the Cycle 1 Day 1 to the earliest date of radiographic disease progression per RECIST 1.1. If a subject did not experience progressive disease, TTP is censored at the last imaging assessment. TTP will be analyzed using the Kaplan-Meier method. The output will include count and percentage of subjects with events or censored outcome including the type of event and censoring. Median TTP and 95% CI based on log-log

transformation will be provided. Landmark analyses at various timepoints may be carried out if of clinical interest. Kaplan-Meier plot supporting the table summary may also be generated.

In addition to TTP by RECIST 1.1 criteria based only on the radiographic assessments, a second definition of TTP which incorporates the clinical progression will be used. The clinical progression is based on the medical review of the reasons of treatment discontinuation or study continuation. If a subject is considered having clinical progression the date of treatment or study discontinuation will be used as date of clinical progression and the TTP is defined as time from Cycle 1 Day 1 to the earliest date of clinical or radiographic disease progression.

### 11.3. Progression-free Survival (PFS)

Progression-free survival is defined as time from Cycle 1 Day 1 to the earliest date of radiographic disease progression per RECIST 1.1 or death, whichever happens first. The detailed event and censoring rules are shown in the table below following the hierarchical order of the logic:

**Table 4: Event and Censoring Rules for PFS**

Situation	Date of Progression or Censoring	Outcome
Death or progression after more than 1 missed imaging visit	Date of last adequate assessment before missed visits	Censored
Death or progression without more than 1 missed visit	Earliest date of death or progression	Event
No Death or progression	Date of last imaging assessment	Censored
No post-baseline assessment	Date of Cycle 1 Day 1	Censored

PFS will be analyzed using the Kaplan-Meier method. The output will include count and percentage of subjects with events or censored outcome including the type of event and censoring. Median PFS and 95% CI based on log-log transformation will be provided. Landmark analyses at various timepoints may be carried out if of clinical interest. Kaplan-Meier plot supporting the table summary may also be generated.

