2.4.2. Missing assessments and inevaluable designation

When no imaging/measurement is done at all at a particular time point, the subject is not evaluable (NE) at that time point. If only a subset of lesion measurements are made at an assessment, usually the case is also considered NE at that time point, unless a convincing argument can be made that the contribution of the individual missing lesion(s) would not change the assigned time point response. This would be most likely to happen in the case of Prod. For example, if a subject had a baseline sum of 50 mm with three measured lesions and at follow-up only two lesions were assessed, but those gave a sum of 80 mm, the subject will have achieved PD status, regardless of the contribution of the missing lesion.

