#### **9.2.4. Analysis Visiting Windows**

No analysis visit window will be defined for safety data or efficacy data except for the tumor marker data. All post-baseline radiological disease assessments will be used for analyses purpose. Nominal clinical visits that are defined in the protocol “Schedule of Event” will be used for summary of safety endpoints. Any unscheduled safety data will not be included in the by-visit summary and will be included in the listings.

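### PFS and TTP are censored at the last scan without requiring that scan to be evaluable, which can carry censored times past the last evidence of no progression

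*SAP*

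**What the plan says.** SAP Table 4 has four rows, applied in order.

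- **Row 1**, an event after more than one missed imaging visit: censor at "Date of last adequate assessment before missed visits".
- **Row 3**, no death or progression: censor at "Date of last imaging assessment".
- **Row 4**, no post-baseline assessment: censor at "Date of Cycle 1 Day 1".

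For TTP, SAP 11.2 says "If a subject did not experience progressive disease, TTP is censored at the last imaging assessment". It has no row for missed visits. The SAP does not define adequate. SAP 9.2.4 adds "All post-baseline radiological disease assessments will be used for analyses purpose", with no exclusion for NE scans.

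Both documents allow a scan to be done and still be NE. Protocol Appendix 2, section 2.4.2, says "If only a subset of lesion measurements are made at an assessment, usually the case is also considered NE at that time point". SAP Table 3 lists NE separately from having no later assessment. Protocol 5.5.1.2 permits palliative radiotherapy and makes irradiated lesions non-evaluable for response.

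SAP 11.1.3 passes the PFS rules on: "The event and censoring rules for DOR will be the same as the rules for PFS". SAP 11.1.4 does the same for duration of stable disease.

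**The concern.** An NE scan establishes neither progression nor its absence. If its date is used for censoring, the subject is counted as progression-free up to a visit at which that was not shown. The subject stays in the Kaplan-Meier risk set for the interval, while a progression in it may go unrecorded. Compared with censoring at the last evaluable scan, the curve can only be higher or unchanged, because the events are the same and the risk sets are at least as large.

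PFS and TTP are listed among the primary endpoints (protocol 3.1.1, SAP 4.1). Medians are planned and landmark estimates are possible, in cohorts of about 20.

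**Working it through.** The plan states no PFS or TTP assumption, so there is no figure of its own to reproduce.

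**1. Two records under the literal rule**

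| Record | As written | Last evaluable evidence |
|---|---|---|
| SD week 8, NE week 16, then off study | week 16 (row 3) | week 8 |
| Only post-baseline scan is NE, at week 8 | about week 8 (row 3; row 4 needs no assessment at all) | Cycle 1 Day 1 |

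Each trailing NE scan adds one scan interval. That is 8 weeks on treatment (6 to 10 with the ±1 week windows) or 16 weeks in long-term follow-up (12 to 20 with ±2 weeks).

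**2. Illustration with 20 subjects (invented data)**

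There are 8, 4 and 2 events at weeks 8, 16 and 24, and two subjects censored at each of those weeks. One of each censored pair ends on an NE scan.

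- As written: (1 − 8/20)(1 − 4/10)(1 − 2/4) = 0.6 × 0.6 × 0.5 = 0.180 at week 24.
- With those three subjects censored one scan earlier: (1 − 8/19)(1 − 4/9)(1 − 2/3) = 0.579 × 0.556 × 0.333 = 0.107.
- The median is 16 weeks under both rules.

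This shows how far the two rules can differ. It does not show which is closer to the truth.

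**3. Bias against a known truth**

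All inputs except the 8-week scan interval are assumptions:

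- exponential time to progression with median 13 weeks
- exponential drop-out with median 30 weeks
- a fraction q of final scans NE regardless of true status, each hiding any progression since the previous scan
- no deaths

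Per scan interval:

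- probability of no progression: s = 2^(−8/13) = 0.653
- probability that a given scan is the last: p = 1 − 2^(−8/30) = 0.169
- true 24-week PFS: s³ = 2^(−24/13) = 0.278

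As written, everyone who reaches a scan is at risk at that scan. A share pq of them have an unreadable final scan, so their progressions are recorded as censored. The apparent hazard is h = (1 − s)(1 − pq), and 24-week PFS tends to (1 − h)³. After the fix those subjects leave the risk set one scan earlier, so h = 1 − s and the estimate tends to 0.278.

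| q | h | (1 − h)³ | Excess, closed form | Simulated, as written | Excess, simulated |
|---|---|---|---|---|---|
| 10% | 0.341 | 0.286 | 0.8 points | 0.284 | 0.6 points |
| 20% | 0.336 | 0.293 | 1.5 points | 0.295 | 1.7 points |
| 40% | 0.324 | 0.309 | 3.1 points | 0.309 | about 3 points |

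Simulated values after the fix are 0.276 to 0.280, within about 0.2 points of the truth. A check with 4,000 cohorts of 20 gave 0.283, 0.295 and 0.309 as written. The estimate's standard deviation at n = 20 is about 13 points, so the Monte Carlo error is 0.13/√4000 = 0.002. The gaps between closed form and simulation are of that order.

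**4. Sensitivity**

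A second simulation used medians of 8 or 16 weeks, a 15% or 30% chance per visit that imaging stops, and 10%, 25% or 50% of final scans NE. The gap between the two rules was 0.6 to 8.0 points at week 16 and 0.6 to 6.8 points at week 24.

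**The case against.** **The direction depends on why scans are NE.** If NE final scans fell only on subjects who had truly not progressed, the rule as written would be unbiased. A run on that basis gives 0.277 to 0.279 against 0.278, and the fix is then too low at 0.258 to 0.272. This stands as a condition: the bias arises only if an NE scan can hide progression. The documents give no reason to suppose that unreadable scans are confined to subjects who have not progressed.

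**A reader might infer that progression cannot be seen at all on an NE scan.** The documents do not support that. Under Appendix 2, Table 1, new lesions or non-target progression make the time point PD whatever target lesions are missing, and section 2.4.2 gives a partly measured case that is PD. What remains exposed is growth in unmeasured target lesions. The figures above let NE hide all progression, so they lie at the high end for a given NE rate.

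**A reader might infer that Table 4 judges the same scan by two standards, or that the SAP expressly counts NE scans.** Neither is stated. Rows 1 and 3 cover mutually exclusive situations, adequate is undefined, and equating it with not-NE is an inference, though the natural one. The fault is a missing condition. TTP has no missed-visit row, so there the point is the missing condition alone.

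**A reader might extend the bias to reported DOR.** SAP Tables 6 to 8 schedule no DOR output, and SAP 11.1.3 says the summary may not be produced. Duration of stable disease appears only in a listing.

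**Nothing is decided on these estimates.** SAP 9.1.2 calls all p-values and intervals supportive. The listings of responses by time point and of PFS would let a reader find a trailing NE scan. Both observations are correct and limit the importance of the point, but they do not supply the missing rule.

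**Conclusion.** The concern holds as a gap in the censoring rule. Followed literally, Table 4 row 3 and SAP 11.2 can count progression-free time past the last evaluable scan, and a subject with only an NE scan is censored near week 8 instead of Cycle 1 Day 1. This can bias Kaplan-Meier PFS and TTP upward.

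The size cannot be taken from the documents. Under the 13-week scenario, 24-week PFS is about 0.6, 1.7 or 3 points too high at 10%, 20% or 40% NE final scans. That is small beside a standard deviation of about 13 points in a cohort of 20. The NE rate, median, drop-out and independence of NE from true status are all assumptions. If no censored subject ends on an NE scan, both rules give the same result. No error rate or power is affected, so this is a minor correction.

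**What to change.** - Define an adequate assessment in SAP 11.3 as one with a time-point response other than NE.
- In Table 4 row 3 and in SAP 11.2 (both TTP definitions), censor at the last adequate assessment.
- Change the situation in row 4 to *no adequate post-baseline assessment*, still censored at Cycle 1 Day 1.

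DOR and duration of stable disease inherit the change through their references to the PFS rules, if they are produced. The cost is a few phrases and one programming filter, with no new data. The downside is slightly shorter censored times for the subjects affected.
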